8.2.1.6. Aim 5 Inclusion Criteria

- Born in 2005 or earlier (as age 18 or older in 2023, owing to the data providing year but not month or day of birth).
- Received a BNT162b2 vaccine and/or seasonal influenza vaccine between 11 September 2023 and end of data.
- At least one year of pharmacy and medical enrollment in HealthVerity prior to index date (earliest vaccination date is index date). A gap of up to 30 days will be allowed.
- 4) Have been a State of California/Louisiana resident for at least one year prior to index date

8.2.2. Exclusion Criteria

Exclusion criteria are specified by each study aim. Within each aim, patients meeting any of the following criteria will not be included in the study:

8.2.2.1. Aim 1 Exclusion Criteria

- Currently pregnant (using a validated gestational age algorithm with up to 9 months lookback) or immunocompromised (using all-available lookback) at the time of study index¹⁸ (code list to be listed in the appendix)
- Individuals with discrepancies in sex and/or year of birth between HealthVerity claims and California/Louisiana immunization registry datasets.
- Persons with a diagnosis of COVID-19 in any setting ≤ 90 days prior to index (FDA EUA date per vaccine)
- Receipt COVID-19 vaccine ≤ 90 days prior to index (FDA EUA date per vaccine)

8.2.2.2. Aim 2 Exclusion Criteria

- Currently pregnant (using a validated gestational age algorithm with up to 9 months lookback) or immunocompromised (using all-available lookback) at the time of study index (code list to be listed in the appendix)
- Individuals with discrepancies in sex and/or year of birth between HealthVerity claims and California/Louisiana immunization registry datasets.
- Persons with a diagnosis of COVID-19 in any setting ≤ 90 days prior to index (FDA EUA date per vaccine and age group)
- Receipt COVID-19 vaccine ≤ 90 days prior to index (FDA EUA date per vaccine)

8.2.2.3. Aim 3A Exclusion Criteria

For each of adult and pediatric:

- Currently pregnant (using a validated gestational age algorithm with up to 9 months lookback) or immunocompromised (using all-available lookback) at the time of study index (code list to be listed in the appendix)
- Individuals with discrepancies in sex and/or year of birth between HealthVerity claims and California/Louisiana immunization registry datasets.
- Individuals who were vaccinated within 13 day of index.
- Individuals who had a change in vaccination status changed during follow-up (i.e. patients who received a vaccination during hospitalization).

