7. RESEARCH QUESTION AND OBJECTIVES

What is the real-world effectiveness of BNT162b2 formulations?

This study is descriptive in nature and as such does not include any pre-specified hypotheses.

Primary objective:

 To evaluate the VE of BNT162b2 formulations in non-pregnant, non-immunocompromised adults against medically attended COVID-19, mortality and healthcare resource utilization by age and adapted vaccine formulation.

Main summary measure: VE = (1 - adjusted hazard ratio [aHR]) * 100, comparing vaccinated to unvaccinated persons

Secondary objectives

 To assess VE of BNT162b2 formulations in pediatrics against medically attended COVID-19, non-COVID-19 respiratory infections, mortality and healthcare resource utilization by age and adapted vaccine formulation.

Main summary measure: VE = (1 - aHR) * 100, comparing vaccinated to unvaccinated persons

To estimate short-term (3A) and long-term (3B) healthcare resource utilization and costs associated with COVID-19 by vaccination status, age, and site of care.

Main summary measure: Inpatient healthcare expenditure comparing vaccinated to unvaccinated persons (3A), and total healthcare expenditure comparing COVID-19 to non-COVID-19 patients (3B).

Exploratory objectives

 To measure VE of BNT162b2 formulations in non-pregnant immunocompromised adults against medically attended COVID-19, mortality and healthcare resource utilization by age and adapted vaccine formulation.

Main summary measure: VE = (1 - aHR) * 100, comparing vaccinated to unvaccinated persons

 To quantify differences in VE of BNT162b2 formulations in non-pregnant, nonimmunocompromised adults when co-administered with seasonal influenza vaccines versus when each vaccine is given separately, by age groups.

> Main summary measure: aRR to evaluate non-inferiority, comparing people with coadministered vaccines to BNT162b2 vaccine alone for COVID-19-related outcomes

> Main summary measure: aRR to evaluate non-inferiority, comparing people with coadministered vaccines to seasonal influenza vaccine alone for influenza-related outcomes

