- A key assumption of the TND is that exposure (here, COVID-19 vaccination) does not impact the probability of selection in the case (a positive test result on a COVID-19 test) or control population (a negative test result on a COVID-19 test). It is possible that vaccinated persons may be less likely to be seek testing in order to become a case than unvaccinated persons. This, if present, would create collider stratification bias via the requirement for testing in a TND, which biases estimates away from the null and may lead to overestimations of VE. 12-14
- Owing to the case-control nature of the design, TND allows for estimation of odds ratios (OR) but not hazard or risk ratios. OR are not directly interpretable as percentage reduction in risk, which is an easily interpretable summary measure of VE. OR with a protective direction of effect (ratio < 1) will underestimate risk, leading to underestimations of VE. 15 A cohort design allows for absolute estimates of risk such as risk differences.

The use of a retrospective cohort study allows for the adoption of design principles of randomized control trials to help mitigate some of these biases.

Cohort identification will begin from the date of EUA or FDA approval for the BNT162b2 formulation. Study follow-up will occur from FDA EUA or approval date until COVID-19 diagnosis or other outcome of interest (hospitalization, emergency department visit, outpatient encounter, end of medical and/or pharmacy enrollment, or death [according to the mortality database]).

In aims 1, 2 and 4, vaccination status will be measured as a time-varying exposure. In aims 3 and 5, vaccination status will be measured as a time-fixed exposure. Exposed person-time begins 14 days after receipt of a BNT162b2 formulation. Unexposed person-time is unvaccinated person-time, as well as 0-13 days after vaccination. The unexposed group will be further stratified by previous vaccination status for relative VE: XBB.1.5 unvaccinated and BA.4/5 vaccinated; XBB.1.5 and BA.4/5 unvaccinated and at least 2 doses of mRNA vaccine (regardless of formulation), never COVID-19 vaccinated.

The full data available, from 01 December 2018, will be used as the look-back period to define patient's characteristics, clinical history, risk factors, and healthcare utilization.

TABLE 2. TARGET TRIAL AND TARGET TRIAL EMULATION

Target Trial Specification ^{16,17}	Target Trial Emulation			
Eligibility criteria				

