8.2.2.4. Aim 3B Exclusion Criteria

For each of adult and pediatric:

- Currently pregnant (using a validated gestational age algorithm with up to 9 months lookback) or immunocompromised (using all-available lookback) at the time of study index (code list to be listed in the appendix)
- Individuals with discrepancies in sex and/or year of birth between HealthVerity claims and California/Louisiana immunization registry datasets.
- Individuals with a diagnosis of COVID-19 in any setting ≤ 90 days prior to index.
- Individuals who were vaccinated within 13 day of index.
- Individuals who had a change in vaccination status changed during follow-up.

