8.7.3. Aim 3A

To estimate short-term healthcare resource utilization and costs associated with COVID-19 by vaccination status, age, and site of care.

Exposure: Persons will be considered vaccinated if they received the XBB.1.5 dose 14 or more days prior to admission. Persons will be considered unvaccinated if they had not received a dose.

Study Period: September 2023 – January 2024

Follow-up time: From admission (index date) to discharge.

Outcomes of interest: Similar to those in Somani, Firestone, Donnelley et al (2023)²²

- Cost of hospitalization
- Average length of stay, in days
- ICU admission
- Receipt of high-flow oxygen or mechanical ventilation
- Inpatient Mortality
- Use of antiviral treatment

Statistical Methods: All analyses will be pooled across California and Louisiana, and stratified by state. Descriptive statistics will be used to summarize patient characteristics, with mean (standard deviation) or median (25th percentile – 75th percentile) for continuous variables and counts (percentages) for categorical variables. Logistic regression will be used to estimate odds ratios (OR, with 95% CI) of ICU admission comparing vaccinated persons to unvaccinated persons. Linear regression with analysis of covariance (ANCOVA) will be used to compare costs of hospitalization for vaccinated and unvaccinated persons, and will be adjusted for age, and baseline characteristics. Results will be stratified by age groups.

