5.2.3. Follow-up

Patients will be followed for between 1 and 12 months after the index date. Patients will be censored at the earliest of: 1) disenrollment from insurance coverage; 2) the date of the first claim with a pregnancy diagnosis in the follow-up; 3) the end of data availability on 30 November 2023 or 4) receipt of COVID vaccination. Control patients may be further censored at the date of the first claim with a COVID-19 diagnosis after 30 November 2022.

A sensitivity analysis will be carried out where COVID-19 patients may be further censored at the date of COVID-19 reinfection. This will be further described in the latter part of the study protocol.

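### Aim 3A excludes patients vaccinated during the hospital stay, so eligibility depends on a post-admission event that falls essentially on the unvaccinated arm

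*Protocol*

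**What the plan says.** Protocol section 8 states: "In aims 3 and 5, vaccination status will be measured as a time-fixed exposure". Protocol 8.7.3 (Aim 3A) ties that exposure to admission: "Persons will be considered vaccinated if they received the XBB.1.5 dose 14 or more days prior to admission", and "Persons will be considered unvaccinated if they had not received a dose". Follow-up in the same section runs "From admission (index date) to discharge".

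The Aim 3A exclusions (Protocol 8.2.2.3) then remove "Individuals who had a change in vaccination status changed during follow-up (i.e. patients who received a vaccination during hospitalization". A separate item removes patients vaccinated within 13 days of index, without saying whether before or after.

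The main summary measure in Protocol section 7 is "Inpatient healthcare expenditure comparing vaccinated to unvaccinated persons (3A". Length of stay, ICU admission and inpatient mortality are further outcomes. Costs are compared by ANCOVA adjusted for age and baseline characteristics. No rationale, expected count or sensitivity analysis accompanies the exclusion.

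Protocol 8.2.2.4 carries a parallel item for Aim 3B: "Individuals who had a change in vaccination status changed during follow-up". The Aim 3B SAP leaves it out of its exclusion list (5.2.2) and instead censors at the earliest of several events, among them "3) the end of data availability on 30 November 2023 or 4) receipt of COVID vaccination".

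**The concern.** With a time-fixed exposure set at admission, who is in the analysis should be settled at admission too. Here it is settled partly by what happens between admission and discharge, the window in which the outcomes accrue.

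Two features make this more than a loss of numbers. First, it is one-sided: a change of status can only run from unvaccinated to vaccinated. Patients dosed shortly before admission are already removed by the 13-day item, so they cannot cross the day-14 line during the stay. Second, a patient must be alive and still an inpatient to be dosed, so removal depends on length of stay, which is itself an outcome and may drive cost.

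At stake is the vaccinated-versus-unvaccinated contrast, including the expenditure measure. Adjusting for variables fixed before admission does not repair selection that occurs after it, and the error does not shrink as the sample grows.

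**Working it through.** The documents give no sample size, in-hospital vaccination rate, stay distribution, mortality or cost per day for Aim 3A, so there is no stated figure to reproduce. The structure follows from the definitions above. The sizes below rest on assumed inputs.

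**Length of stay, closed form.** Assume exponential stays with mean m = 6 days and a constant daily chance h of a dose while in hospital.

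- Share of the unvaccinated arm dropped: f = hm/(1 + hm)
- Mean stay of those kept: m/(1 + hm)
- Mean stay of those dropped: m(2 + hm)/(1 + hm)

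| h per day | f | mean stay kept | mean stay dropped |
|---|---|---|---|
| 0.2% | 0.012/1.012 = 1.2% | 6/1.012 = 5.93 | 11.9 |
| 0.5% | 0.03/1.03 = 2.9% | 6/1.03 = 5.83 | 11.8 |
| 1% | 0.06/1.06 = 5.7% | 6/1.06 = 5.66 | 11.7 |

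The dropped stays are nearly twice the average, and the relative fall in mean stay equals f. For small h, the fall is about f times the squared coefficient of variation of stay, which is 1 for an exponential. A heavier tail would raise it and a lighter one would lower it.

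**Stay, cost and ICU, by simulation under no true difference.** Assumptions: 1,000,000 unvaccinated admissions; stay of half a day plus an exponential with mean 6 (about 6.5 days overall); cost of 5000 + 2500 per day; ICU probability rising with stay; doses at a constant daily rate among eventual survivors.

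| f | mean stay | mean cost | null ICU odds ratio, vaccinated vs unvaccinated |
|---|---|---|---|
| 0.1% | −0.08% | −0.06% | 1.00 |
| 1% | −0.85% | −0.65% | 1.01 |
| 5% | −4.2% | −3.2% | 1.04 |
| 10% | −8.4% | −6.4% | 1.09–1.10 |

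Cost moves less than stay even with an explicit per-day component, because part of the assumed cost is fixed: 0.85% × 16,250/21,250 = 0.65%. If doses are given at discharge, unrelated to stay, neither stay nor cost moves.

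**Mortality, three mechanisms, true value 10%.**

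- Doses only to patients who survive: observed mortality = 10%/(1 − f). At f = 1% this is 10.10%; at 5%, 10.53%.
- Constant daily rate, with death unrelated to stay: no change beyond simulation noise.
- Constant rate of 0.5% per day, with mean stay 9 days in those who die and 5.7 in survivors (0.1 × 9 + 0.9 × 5.7 = 6.03 overall): kept fractions are 1/1.045 and 1/1.0285, so mortality = (0.1/1.045)/(0.1/1.045 + 0.9/1.0285) = 0.0957/0.9708 = 9.86%.

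Mortality can therefore rise, stay the same or fall.

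**Without the exclusion.** If everyone stays in the arm set at admission, this selection bias is zero by construction, whatever the in-hospital vaccination rate.

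**The case against.** The strongest reply is that the effect is probably tiny. Every Aim 3A patient is admitted with COVID-19 as principal diagnosis (Protocol 8.2.1.3), and Protocol Table 2 treats 90 days after a COVID-19 diagnosis as a reasonable point from which people are again at risk and eligible for vaccination. Doses during the acute admission may therefore be exceptional. This stands as a point about size. It gives no rate, and it also means that the exclusion achieves little.

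Four stronger readings are tempting, and the documents do not support them.

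- **Unvaccinated mortality is necessarily overstated.** It is not. A patient dosed in hospital who later dies there is also removed, and the direction depends on when doses are given and to whom.
- **Cost shifts in proportion to stay.** Protocol Table 4 derives hospitalization cost from a proxy algorithm built on Medicare prospective payment schedules. Nothing in the documents prices a day of stay.
- **Only unvaccinated patients can ever be removed.** That follows from a change of status, but the bracketed explanation names no vaccine. Read alone, it could also catch a vaccinated patient given a further dose. Hence "essentially" is as far as the text goes.
- **The Aim 3B SAP is a clean model.** It censors at vaccination (5.2.3) and requires at least one month of follow-up (5.2.1.1 and 5.2.1.2). Together these may still select on early vaccination.

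It is also fair to say that the rule may not survive. The supplied SAPs cover Aims 1, 2 and 3B, and Protocol 8.7 lets a SAP modify the protocol. Whether an Aim 3A SAP keeps the exclusion cannot be seen.

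**Conclusion.** The point holds as a design flaw of undetermined and possibly small size. Protocol 8.2.2.3 conditions eligibility on a post-admission event, acts essentially on the unvaccinated arm, and requires the patient to be alive and in hospital.

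If doses are likelier in longer stays, that arm's mean stay is understated, and its cost is understated to the extent that cost rises with stay. Any saving associated with vaccination would then be understated. No direction can be claimed for mortality.

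The distortion is roughly proportional to the share vaccinated in hospital: about 1% or less in relative terms if that share is 1% or less, and about 4% for stay at a share of 5%. These sizes assume stays about as variable as an exponential distribution and the dosing mechanisms described. None of those inputs is in the documents.

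**What to change.** In Protocol 8.2.2.3, and in any Aim 3A SAP:

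1. Delete the exclusion for a change of vaccination status during the stay, and analyse every patient by status at admission.
2. Limit the 13-day exclusion explicitly to doses given before the index date, as Aim 3B SAP 5.2.2 does. Otherwise a dose soon after admission could trigger it and bring the same selection back.
3. Report the number vaccinated in hospital by arm, so that readers can judge the size.
4. If the exclusion is wanted at all, run it only as a sensitivity analysis.

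This costs a change of wording and one extra count. It adds patients to the analysis and needs no new data.

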8.2.2.4. Aim 3B Exclusion Criteria

For each of adult and pediatric:

- Currently pregnant (using a validated gestational age algorithm with up to 9 months lookback) or immunocompromised (using all-available lookback) at the time of study index (code list to be listed in the appendix)
- Individuals with discrepancies in sex and/or year of birth between HealthVerity claims and California/Louisiana immunization registry datasets.
- Individuals with a diagnosis of COVID-19 in any setting ≤ 90 days prior to index.
- Individuals who were vaccinated within 13 day of index.
- Individuals who had a change in vaccination status changed during follow-up.

8.2.2.5. Aim 4 Exclusion Criteria

- Currently pregnant (using a validated gestational age algorithm with up to 9 months lookback) at the time of study index (code list to be listed in the appendix)
- Individuals with discrepancies in sex and/or year of birth between HealthVerity claims and California/Louisiana immunization registry datasets.
- Persons with a diagnosis of COVID-19 in any setting ≤90 days prior to index (FDA EUA date per vaccine)
- Receipt COVID-19 vaccine ≤ 90 days prior to index (FDA EUA date per vaccine)

8.2.2.6. Aim 5 Exclusion Criteria

 Currently pregnant (using a validated gestational age algorithm with up to 9 months lookback) or immunocompromised (using all-available lookback) at the time of study index (code list to be listed in the appendix)

- Individuals with discrepancies in sex and/or year of birth between HealthVerity claims and California/Louisiana immunization registry datasets.
- Died, disenrolled, had a COVID-19 or influenza diagnosis, or received a second dose of either vaccine ≤14 days after their first dose
- Persons with a diagnosis of COVID-19 in any setting ≤90 days prior to index (vaccination date)
- Received influenza vaccine between August 1-September 10, 2023, as these persons are not at risk of coadministration with an XBB.1.5 monovalent vaccine given this period predates its availability.
- 6) Received any type of COVID-19 vaccine other than BNT162b2 XBB.1.5 on the index date
- For patients >=65, had a standard dose influenza vaccine or unknown type influenza vaccine.

8.3. Variables

TABLE 3. EXPOSURE VARIABLES

Variable	Data source(s)	Operational definition
BNT162b2 XBB.1.5 mRNA vaccine after FDA authorization date and 14 or more days	California/Louisiana Immunization Registry as well as HV Claims	Vaccines will be enumerated as per section 8.2. Date of vaccination will be used to assess time-based inclusion/exclusion criteria.
BNT162b2 BA.4/5 mRNA vaccine after FDA authorization date and 14 or more days	California/Louisiana Immunization Registry as well as HV Claims	Vaccines will be enumerated as per section 8.2. Date of vaccination will be used to assess time-based inclusion/exclusion criteria.
Influenza vaccine	HV Claims	Identified using NDC or CPT code

TABLE 4. OUTCOME VARIABLES

Variable	Data source(s)	Operational definition
COVID-19 diagnosis	HV Claims	Any encounter regardless of diagnosis position or setting with ICD-10-CM code: U07.1
COVID-19 hospitalization	HV Claims	Inpatient encounter at an acute care facility with ICD-10-CM code: U07.1 "COVID-19" listed in any diagnosis position
COVID-19 emergency department visit	HV Claims	Emergency department visit with ICD-10-CM code: U07.1

Variable	Data source(s)	Operational definition
COVID-19 outpatient encounter	HV Claims	Outpatient encounter with ICD-10-CM code: U07.1
COVID-19 critical illness	HV Claims	Intensive care unit [ICU] admission, mechanical ventilation, or inpatient death
All-cause mortality	HV Mortality Database	HealthVerity ID in Mortality Database
Non-COVID-19 respiratory infections (pneumonia, RSV, rhinovirus, antibiotic prescriptions)	HV Claims	Any encounter regardless of setting with ICD-10- CM code for diagnosis or NDC codes for antibiotics (Codes in Annex)
Hospitalization length of stay (days)	HV Claims	Date of service end – date of service
ICU admission	HV Claims	As per HealthVerity's suggestion, ICU related services/inpatient stays will be found on Institutional claims, and can be identified using revenue codes (codes in Annex).
Invasive ventilation	HV Claims	CPT, HCPCS and ICD-10 (codes in Annex)
Cost of hospitalization	HV Claims	Using HealthVerity's "Proxy Financial Algorithm", based on CMS Medicare prospective payment system fee schedules
Influenza diagnosis	HV Claims	Any encounter regardless of setting with ICD-10- CM code: J09-J11
Influenza hospitalization	HV Claims	Inpatient encounter with ICD-10-CM code: J09- J11 listed as in any diagnosis position
Influenza emergency department visit	HV Claims	Emergency department visit with ICD-10-CM code: J09-J11
Influenza outpatient encounter	HV Claims	Outpatient encounter with ICD-10-CM code: J09-J11
Negative control outcome, such as accidental injury, ingrown toenail or atopic dermatitis	HV Claims	Any encounter regardless of setting, with ICD- 10-CM code for negative control outcomes (codes in annex)

TABLE 5. COVARIATES

Variable	Data source(s)	Operational definition
		Age assessed at index date. Where not stratified, age will be adjusted as:
	HV	For aims 1 and 4, age will be directly adjusted using indicator variables for 18-49, 50-64 and 65+.
Age	Claims/CAR	For aim 2, age will be directly adjusted using indicator variables for <5 years, 5-11 and 12-17 years.
		For aim 5, age will be included in the propensity score as a continuous variable.
Sex	HV Claims/CAR	Sex assessed at index date as male, female or unknown. Models will be adjusted for sex when not stratified by sex.
State of residence	HV Claims	Models will be adjusted for state (California or Louisiana), except those which are stratified by state.

disease, or cardiomyopathies HV Claims He Mental health conditions: mood disorders including depression; Schizophrenia spectrum disorders Neurologic conditions limited to dementia Obesity (BMI ≥30 kg/m² or ≥95 th percentile in children) Physical inactivity Primary immunodeficiencies Smoking, current and former Solid organ or blood stem transplantation Tuberculosis Use of corticosteroids or other immunosuppressive medications Note: racial/ethnic minority status is included in the high risk definition, but not included in HealthVerity data and therefore unable to be	HV Claims	 Cystic fibrosis Diabetes mellitus, type 1 Diabetes mellitus, type 2 Disabilities, including Down syndrome Heart conditions: heart failure, coronary artery disease, or cardiomyopathies HIV Mental health conditions: mood disorders including depression; Schizophrenia spectrum disorders Neurologic conditions limited to dementia Obesity (BMI ≥30 kg/m² or ≥95th percentile in children) Physical inactivity Primary immunodeficiencies Smoking, current and former Solid organ or blood stem transplantation Tuberculosis Use of corticosteroids or other immunosuppressive medications Note: racial/ethnic minority status is included in the high risk definition, but not included in HealthVerity data and therefore unable to be
the high risk definition, but not included in HealthVerity data and therefore unable to be assessed. Pregnancy is included in the high risk definition, but is an exclusion criteria for each aim in this protocol and therefore is not listed here. Given the nature of administrative claims data,		the high risk definition, but not included in HealthVerity data and therefore unable to be assessed. Pregnancy is included in the high risk definition, but is an exclusion criteria for each aim in this protocol and therefore is not listed here. Given the nature of administrative claims data, obesity, physical inactivity, and smoking are likely

Variable	Data source(s)	Operational definition
Charlson-Deyo Comorbidity Index, ²⁵ operationalized as scores of 0, 1 or 2 using	HV Claims	Assessed using all-available lookback data. Codes are in annex, and conditions are scored as: 1 point for each of: Myocardial infarction CHF Peripheral vascular disease Cerebrovascular disease Dementia Chronic pulmonary disease Connective tissue disease Peptic ulcer disease Mild liver disease Diabetes mellitus without chronic complications 2 points for each of: Hemiplegia Moderate to severe renal disease Diabetes with chronic complications Cancer, including leukemia and lymphoma 3 points for moderate or severe liver disease 6 points for each of: Metastatic carcinoma HIV/AIDS
Receipt of skilled nursing care and/or long-term care facility stay in year prior to index	HV Claims	Codes in Annex
Wellness visit	HV Claims	Codes in Annex
Decreased functional status	HV Claims	Codes in Annex
Influenza vaccination in year prior to index	HV Claims	Vaccines will be enumerated as per section 8.2. Influenza vaccines are recommended annually, and therefore we will measure influenza vaccination in prior year.

Variable	Data source(s)	Operational definition
Pneumococcal vaccination using all-available time prior to index	HV Claims	Vaccines will be enumerated as per section 8.2. Pneumococcal vaccinations are generally not repeated events, and therefore we will use allavailable lookback data to assess receipt.
Herpes zoster vaccination using all-available time prior to index	HV Claims	Vaccines will be enumerated as per section 8.2. Herpes zoster vaccinations are generally not repeated after primary series, and therefore we will use all-available lookback data to assess receipt.
Outpatient visits prior to index	HV Claims	Number of outpatient visit(s) in 180 days prior to index
Inpatient admission(s) prior to index	HV Claims	Number of inpatient admission(s) in 180 days prior to index
Telehealth visits prior to index	HV Claims	Number of telehealth encounters (CPT: 99201- 99215) in 180 days prior to index
Number of documented SARS-CoV-2 tests in the 180 days prior to index	HV Claims	Number of visits in any setting with CPT: 86408, 86409, 0225U, 0226U
Prior post-COVID-19 conditions	HV Claims	Using all-available lookback data, any encounter regardless of setting with ICD-10-CM U09.9 "Post-COVID-19 condition"
For aim 5 only (coadministration): Number of documented influenza tests in the 180 days prior to index	HV Claims	Number of visits in any setting with CPT: 87400
For aim 5 only (coadministration): Lipid and/or HbA1C labs in the 180 days prior to index	HV Claims	Encounter with CPT: A56686. These labs were selected as potential measures of health system usage, as people who monitor their lipids or blood glucose may share some behaviors as vaccinations. We are able to incorporate this in propensity score adjusted analyses (aim 5) but not analyses with direct adjustment (aim 1, 2 and 4), given the need for smaller sets of covariates.
For aim 5 only (coadministration): vaccine administration setting	California /Louisiana Vaccine Registry	As pharmacy, doctor's office, or other.

